6 STUDY INTERVENTION

Study treatment is defined as any IP(s) (including marketed product comparator and placebo) or medical device(s) intended to be administered to a study participant according to the study protocol. Study treatment in this study refers to osimertinib and/or savolitinib.

6.1 Study Intervention(s) administered

6.1.1 Investigational products

Refer to [Table 6](#) for information regarding the study treatments.

Table 6 **Study treatments**

	Osimertinib/Placebo to Osimertinib	Savolitinib
Dosage formulation:	80 mg osimertinib/placebo to osimertinib (1 × 80 mg tablet once daily) 40 mg osimertinib/placebo tablets are available if a dose reduction is required	300 mg savolitinib once daily CCI OR 600 mg savolitinib once daily CCI OR 300 mg savolitinib twice daily CCI
Route of administration:	Oral	Oral
Dosing instructions:	Osimertinib/placebo to osimertinib will be administered once daily with or without food except for the day on which PK samples are taken when osimertinib will be taken after a meal prepared by the clinic. Doses should be taken approximately 24 hours apart at the same time point each day. Doses should not be missed. If a patient misses taking a scheduled dose, within a window of 12 hours, it is acceptable to take the dose. If it is more than 12 hours after the scheduled dose time, the missed dose should not be taken, and patients should be instructed to take the next dose at the next scheduled time. If a patient vomits after taking their study drug, they should not make up for this dose, but should take the dose at the next scheduled time.	Savolitinib will be taken once daily or twice daily within 15 minutes after the start of a meal except for the day on which PK samples are taken when savolitinib will be taken after a meal prepared by the clinic. Doses should not be missed. If a patient vomits after taking their study drug, they should not make up for this dose, but should take the next dose at the next scheduled time. Once daily dosing: Doses should be taken approximately 24 hours apart at the same time point each day. If a patient misses taking a scheduled dose, within a window of 12 hours, it is acceptable to take the dose. If it is more than 12 hours after the scheduled dose time, the missed dose should not be taken, and patients should be instructed to take the next dose at the next scheduled time. Twice daily dosing: Doses should be taken approximately 12 hours apart at the same time point each day. If a patient misses taking a scheduled dose, within a window of 6 hours, it is acceptable to take the dose. If it is more than 6 hours after the scheduled dose time, the missed dose should not be taken, and patients should be instructed to take the next dose at the next scheduled time.
Packaging and labelling:	Study treatment will be provided in HDPE bottles with child resistant closures. Each package will be labelled in accordance with Good Manufacturing Practice (GMP) Annex 13 and per country regulatory requirement.	Study treatment will be provided in HDPE bottles with child resistant closures. Each bottle will be labelled in accordance with Good Manufacturing Practice (GMP) Annex 13 and per country regulatory requirement.

Table 6 **Study treatments**

	Osimertinib/Placebo to Osimertinib	Savolitinib
IMP or NIMP/AxMP	IMP	IMP
Provider:	AstraZeneca	AstraZeneca

AxMP Auxilliary medicinal product; eCRF Electronic Case Report Form; HDPE High-density polyethylene; IMP investigational medicinal product; NIMP Non-investigational medicinal product; PK Pharmacokinetics.

6.2 Preparation/handling/storage/accountability of interventions

The investigator or designee must confirm appropriate temperature conditions have been maintained during transit for all study treatment received and any discrepancies are reported and resolved before use of the study treatment.

Only patients enrolled in the study may receive study treatment and only authorised site staff may dispense study treatment. All study treatments must be stored in a secure, environmentally controlled, and monitored (manual or automated) area in accordance with the labelled storage conditions with access limited to the investigator and authorised site staff.

The investigator, institution or the head of the medical institution (where applicable) is responsible for study treatment accountability, reconciliation, and record maintenance (ie, receipt, reconciliation and final disposition records).

Further guidance and information for the final disposition of unused study treatment are provided in the Central Laboratory Manual.

6.3 Measures to minimise bias: randomisation and blinding

Patients who sign the ICF for pre-screening MET status testing will be registered in an interactive web response system (IWRS) to receive an E code. Patients who have tumour MET-status subsequently assessed as eligible for the study will be registered as eligible in the IWRS prior to starting study treatment. Before the study is initiated, the log-in information and directions for the IWRS will be provided to each site.

Patients will complete treatments as specified above or until objective disease progression, unacceptable toxicity occurs, consent is withdrawn, or another discontinuation criterion is met.

If a patient withdraws from the study, then his/her enrolment code cannot be reused. Withdrawn patients will not be replaced.

Patients enrolled under CSP versions 1.0 to 6.0

Patients enrolled under CSP versions 1.0 to 5.0 who had tumour MET-status subsequently assessed as eligible for the study were registered as eligible in the IWRS prior to starting study treatment.

Under CSP versions 5.0 and 6.0, patients were centrally assigned to randomised study intervention (300 mg bid and 600 mg od regimens), using IWRS. Before recruitment for the 300 mg bid and 600 mg od regimens was initiated, the telephone number and call-in directions and/or the log in information and directions for the IWRS were provided to each site. The site was to contact the IWRS prior to the start of study intervention administration for each patient and record the intervention assignment on the applicable eCRF for patients receiving open-label treatment, if required.

Patients enrolled under CSP version 7.0

Under CSP version 7.0, all patients will be centrally assigned to randomised study intervention (savolitinib 300 mg bid + osimertinib or savolitinib 300 mg bid + placebo) using IWRS. Before recruitment is initiated, the telephone number and call-in directions and/or the log in information and directions for the IWRS will be provided to each site.

Patients randomised to the savolitinib 300 mg bid + placebo arm may cross over to savolitinib 300 mg bid plus osimertinib 80 mg od following investigator assessment of PD per RECIST 1.1. Once the investigator has documented progression in the eCRF, and obtained approval for unblinding from the study physician, the treatment code for a patient may be obtained from the IWRS via a dedicated option they may select in this situation. In all other circumstances the treatment code should not be unblinded except in medical emergencies when the appropriate management of the patient requires knowledge of the treatment allocation. The investigator documents and reports the action to the AstraZeneca study physician, without involvement of other personnel to maintain study integrity.

AstraZeneca retains the right to break the code for SAEs that are unexpected and are suspected to be causally related to an investigational product and that potentially require expedited reporting to regulatory authorities.

Treatment codes will not be unblinded for the planned analyses of data until all decisions on the evaluability of the data from each individual patient have been made and documented.

The IWRS will be programmed with blind-breaking instructions. In case of an emergency, in which the knowledge of the specific blinded study intervention will affect the immediate management of the patient's condition (eg, antidote available), the investigator has the sole responsibility for determining if unblinding of a patients' treatment assignment is warranted. Patient safety must always be the first consideration in making such a determination. If a patient's treatment assignment is unblinded, the sponsor must be notified within 24 hours after

breaking the blind. The investigator documents and reports the action to the AstraZeneca physician, without involvement of other personnel to maintain study integrity. Additionally, patients with investigator-assessed objective PD may be unblinded.

The personnel analysing the PK samples will be unblinded to the investigational treatment for each patient.

The AstraZeneca study team will be unblinded at the time of the primary analysis. Site staff and patients will remain blinded until database lock for the final analysis.

6.4 Study intervention compliance

The study medication should only be used as directed in this protocol. Details of treatment with study medication for each patient will be recorded in the appropriate sections in the eCRF. Treatment compliance will be assessed by the tablet or capsule count and the information should be recorded in the appropriate section of the eCRF.

Patients should return all unused medication and empty containers to the investigator.

The study personnel at the investigational site will account for all drugs dispensed and for appropriate destruction. Certificates of delivery and destruction should be signed.

It is the investigator/institution's responsibility to establish a system for handling study treatments, including IPs, so as to ensure that:

- Deliveries of such products from AstraZeneca or its representative are correctly received by a responsible person.
- Such deliveries are recorded.
- Study treatments are handled and stored safely and properly as stated on the label.
- Study treatments are only dispensed to study patients in accordance with the protocol.

The study personnel will account for all study drugs dispensed to and returned from the patient.

At the end of the study, it must be possible to reconcile delivery records with records of usage and destroyed/returned stock. Records of usage should include the identification of the person to whom the study treatment was dispensed, the quantity and date of dispensing and unused study treatment returned to the investigator. This record is in addition to any drug accountability information recorded on the eCRF. Any discrepancies must be accounted for on the appropriate forms. Certificates of delivery and return must be signed, preferably by the investigator or a pharmacist, and copies retained in the investigator site file.

Dispensing and accountability records will continue to be collected for as long as patients continue to receive study treatment, although they will not be entered on the eCRF after the database has closed.

Any change from the dosing schedule, dose interruptions, dose reductions, dose discontinuations should be recorded in eCRF.

Study site personnel, if applicable, or the AstraZeneca monitor will account for all study drugs received at the site, unused study drugs and for appropriate destruction. Certificates of delivery, and destruction should be signed.

6.5 Concomitant therapy

Any medication or vaccine including over-the-counter or prescription medicines, vitamins, and/or herbal supplements that the patient is receiving at the time of enrolment or receives within 4 weeks prior to the first dose, during the study, and until the 28 day follow-up visit must be recorded along with:

- Reason for use.
- Dates of administration including start and end dates.
- Dosage information including dose and frequency.

In addition, for patients continuing treatment with osimertinib during Screening the date and time of administration of the last dose of osimertinib prior to Cycle 1 Day 1 (prior to PK sampling) should be recorded.

Medication other than that described in [Appendix J](#), which is considered necessary for the patient's safety and wellbeing, may be given at the discretion of the investigator and recorded in the appropriate sections of the eCRF.

The use of medications listed in [Table 7](#) is restricted, these medications are permitted with caution and careful monitoring of patients.

Table 7 **Restricted medications**

Medication/class of drug:	Usage (including limits for duration permitted and special situations in which it's allowed)
Paracetamol	The administration of acetaminophen (paracetamol) to a patient is restricted to 3 g per day or the maximum dose approved locally (if less than 3 g/day) during the study.
Sensitive CYP2C8, CYP2C9, and CYP2D6 substrates	In vitro savolitinib is an inhibitor of CYP2C8, CYP2C9, and CYP2D6. Those drugs defined as sensitive CYP2C8, CYP2C9, and CYP2D6 substrates (almost exclusively metabolised by these enzymes should be used with caution when co-dosed with savolitinib.

Table 7 Restricted medications

Medication/class of drug:	Usage (including limits for duration permitted and special situations in which it's allowed)
Sensitive CCI substrates.	Those drugs defined as sensitive CCI substrates should be used with caution when co-dosed with savolitinib.
Drugs affected by P-glycoprotein	Drugs that are known to be affected by P-glycoprotein such as digoxin, quinidine, loperamide, ritonavir and saquinavir should be used with caution.
Warfarin	The use of warfarin for oral anticoagulation is not recommended. Patients who are taking warfarin should be monitored closely for INR changes.
Metformin	Use with caution, monitor patients for the effect of increased metformin exposure.
Adefovir, lamivudine and tenofovir	Use with caution, monitor patients for the effect of increased exposure.
Drugs whose disposition is dependent upon the Breast Cancer Resistance Protein	
Patients taking concomitant medications whose disposition is dependent upon the Breast Cancer Resistance Protein and with a narrow therapeutic index should be closely monitored for signs of changed tolerability as a result of increased exposure of the concomitant medication whilst receiving osimertinib.
 
Patients taking rosuvastatin should have creatine phosphokinase levels monitored (due to Breast Cancer Resistance Protein-mediated increase in exposure). If the patient experiences any potentially relevant adverse events suggestive of muscle toxicity including unexplained muscle pain, tenderness, or weakness, particularly if accompanied by malaise or fever, rosuvastatin must be stopped and any appropriate further management should be taken.

Drugs prolonging QT interval	
The concomitant administration of drugs known to prolong QT interval is restricted unless considered essential due to patient management, in which case, patients should be closely monitored with more frequent ECGs. Additional guidance on drugs known to prolong QT interval is provided in Appendix J.
 
The following drugs are known to prolong QT interval or induce Torsades de Pointes and should not be combined with osimertinib: Clarithromycin, droperidol, erythromycin, procainamide, cisapride, disopyramide, dofetilide, domperidone, ibutilide, quinidine, sotalol, sparfloxacin, thioridazine, bepridil, chlorpromazine, halofantrine, haloperidol, mesoridazine, levomethadyl, methadone, pimozide, arsenic trioxide, pentamidine, amiodarone, chloroquine.
 
See Appendix J.

Table 7 Restricted medications

Medication/class of drug:	Usage (including limits for duration permitted and special situations in which it's allowed)
Drugs that may possibly prolong QT interval	
The use of the following drugs is permitted (notwithstanding other exclusions and restrictions) provided the patient has been stable on therapy for the periods indicated:
 
Alfuzosin, chloral hydrate, ciprofloxacin, dolasetron, foscarnet, galantamine, gemifloxacin, isridipine, ketoconazole, levofloxacin, mexiletine, nicardipine, octreotide, ofloxacin, ondansetron, quetiapine, ranolazine, telithromycin, tizanidine, vardenafil, venlafaxine, ziprasidone.
 
Amantadine, amitriptyline, amoxapine, clozapine, doxepin, felbamate, flecainide, fluconazole, fosphenytoin, gatifloxacin, granisetron, imipramine, indapamide, lithium, moexipril/HCTZ, moxifloxacin, risperidone, roxithromycin, sertraline, trimethoprim-sulfa, trimipramine, voriconazole.
 
Azithromycin, citalopram, clomipramine, itraconazole, nortriptyline, paroxetine, solifenacain, tacrolimus
 
Fluoxetine, protriptyline, tamoxifen. See Appendix J.

Guidance on medicines to avoid, medications that require close monitoring, and washout periods is provided in [Appendix J](#) and a list of medicines to avoid is kept up to date at the following: <http://medicine.iupui.edu/clinpharm/ddis/main-table>.

Other medication other than that described above, including denosumab, corticosteroids and/or bisphosphonates for the treatment of bone metastases, which is considered necessary for the patient's safety and wellbeing, may be given at the discretion of the investigator and recorded in the appropriate sections of the eCRF.

6.5.1 Rescue Medicine

Recommendations on rescue medicine, regarding hypersensitivity management or pre-treatment for such reactions and other AE management or prophylaxis are provided in [Appendix I](#).

The study site will supply required rescue medication that will be obtained locally.

Although the use of rescue medications is allowable at any time during the study, the period of delay in rescue medication following study intervention will be decided based on study investigator's discretion. The date and time of rescue medication administration as well as the name and dosage regimen of the rescue medication must be recorded.

6.6 Dose modification

Dose modifications of one or both agents are decided by the investigator (following discussion with AstraZeneca when needed) based on the type of AEs and the known adverse drug reactions for each drug. In case a dose reduction is necessary, the study treatments will be administered as follows:

Table 8 Dose reduction for osimertinib (or placebo to osimertinib) to manage adverse events

Starting osimertinib (or placebo) dose	80 mg od (1 × 80 mg tablet once daily)
Reduced dose -1	40 mg od (1 × 40 mg tablet once daily)

od Once daily.

Table 9 Dose reduction for savolitinib to manage adverse events

Starting savolitinib dose	300 mg bid	300 mg od	600 mg od
Reduced dose -1			
Reduced dose -2			

Note: Only 2 dose reductions of savolitinib are permitted.

Bid Twice daily; od Once daily.

For guidance on dose modifications for management of AEs for osimertinib and savolitinib, see [Appendix I](#).

6.6.1 Meals and dietary restrictions

Refer to Section [5.3.1](#) for details of meals and dietary restrictions.

6.7 Intervention after the end of the study

After the final DCO, the clinical study database will be closed to new data. Patients receiving study treatment at the time of the final data cut will be able to continue to receive study treatment (either combination or monotherapy) as long as, in the opinion of the investigator, they are still receiving clinical benefit.

Patients who remain on study treatment after the final analysis will be monitored according to routine clinical practice as defined by the investigator. Study treatment will be supplied to sites manually outside of the IWRS. Drug dispensation and reconciliation will be handled by

site on each patient's visit. Paper form process will be used for SAE reporting, all SAEs, overdoses and pregnancies will be reported until 30 days after the last dose. The study will remain open until last patient treated. Last patient last visit will be defined as the last patient's treatment discontinuation.

In the event that product development reaches a point where alternative product supply options become available, then these alternative product supply options will be discussed by AstraZeneca with the investigator. AstraZeneca will work with the investigator to transition the patients to alternative supply, where possible.

In the event that a roll-over study is available at the time of the final DCO and database closure, patients currently receiving study treatment may be transitioned to such a study, and the current study would reach its end. The roll-over study would ensure treatment continuation with visits assessment per its protocol. Any patient that would be proposed to move to such study would be given a new Informed Consent.

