 - Women under the age of 50 years would be considered postmenopausal if they have been amenorrhoeic for 12 months or more following cessation of exogenous hormonal treatments and with luteinizing hormone and follicle stimulating hormone levels in the post-menopausal range for the institution.
 - Documentation of irreversible surgical sterilisation by hysterectomy, bilateral oophorectomy or bilateral salpingectomy but not tubal ligation.

Further information is available in [Appendix G](#) (Definition of Women of Childbearing Potential and Acceptable Contraceptive Methods).

- 19 Male patients with a female partner of childbearing potential should be willing to use barrier contraception during the study and for 6 months following discontinuation of study drug. Patients should refrain from donating sperm from the start of dosing until 6 months after discontinuing study treatment.

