5.3.2 Pregnancy and contraception

Women of childbearing potential

Females of childbearing potential should use highly effective methods of contraception from the time of screening until 6 weeks after discontinuing study treatment. Acceptable methods of contraception include full abstinence, tubal ligation, combined oral, transdermal or intra-vaginal hormonal contraceptives, medroxyprogesterone injections (eg, Depo-provera), copper-banded intra-uterine devices, hormone impregnated intra-uterine systems and vasectomised partners (see [Appendix G](#)). All methods of contraception (with the exception of total abstinence) should be used in combination with the use of a condom by their male sexual partner for intercourse.

Males

Male patients must use a condom during sexual intercourse with a female partner of childbearing potential during the study and for 24 weeks after discontinuing study treatment. If the partner is not of childbearing potential, male patients should use a condom during the study and for 5 elimination half-lives afterwards (48 hours after last dose of savolitinib) with all sexual partners.

Male patients should refrain from donating sperm from the start of dosing until 24 weeks after discontinuing study treatment.

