8.4.2.2 Paternal exposure

Male patients should refrain from fathering a child or donating sperm during the study and 6 months following the last dose.

Pregnancy of the patient's partner is not considered to be an AE. However, the outcome of all pregnancies (spontaneous miscarriage, elective termination, ectopic pregnancy, normal birth or congenital abnormality), occurring from the date of the first dose until 6 months after the last dose and as indicated by previous studies (pre-clinical and clinical) should, if possible, be followed up and documented in the Pregnancy Report Form. Consent from the partner must be obtained before the Pregnancy Report Form is completed.

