Investigators and sub-investigators will provide the sponsor with sufficient, accurate financial information as requested to allow the sponsor to submit complete and accurate financial certification or disclosure statements to the appropriate regulatory authorities. Investigators

are responsible for providing information on financial interests during the course of the study and for 1 year after completion of the study.

A 3 Informed consent process

The investigator or his/her representative will explain the nature of the study to the patient or his/her legally authorised representative and answer all questions regarding the study.

Patients must be informed that their participation is voluntary. Patients or their legally authorised will be required to sign a statement of informed consent that meets the requirements of 21 CFR 50, local regulations, ICH guidelines, Health Insurance Portability and Accountability Act (HIPAA) requirements, where applicable, and the IRB/IEC or study centre.

The medical record must include a statement that written informed consent was obtained before the patient was enrolled in the study and the date and time the written consent was obtained. The authorised person obtaining the informed consent must also sign the ICF.

Patients must be re-consented to the most current version of the ICF(s) during their participation in the study.

A copy of the ICF(s) must be provided to the patient or the patient's legally authorised representative.

If a patient declines to participate in any voluntary exploratory genetic research component of the study, there will be no penalty or loss of benefit to the patient and he/she will not be excluded from other aspects of the study.

If a patients' partner becomes pregnant during or within 6 months after the study, the partner is asked to sign the "Adult Study Informed Consent Form for Pregnant Partners of Study Patients" and provide information about the pregnancy accordingly.

A patient who is rescreened is not required to sign another ICF if the rescreening occurs within the screening window.

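### After the final cut-off, Section 6.7 stops pregnancy reporting 30 days after the last dose, before the protocol's own 6-week and 6-month windows close; male precautions are also 24 weeks in one section and 6 months in others.

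*Protocol*

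**What the plan says.** **Reporting after the final cut-off.** Protocol Section 6.7 covers patients who stay on study treatment once the database has closed. Reporting moves to paper, and "all SAEs, overdoses and pregnancies will be reported until 30 days after the last dose". No exception is named and no other section is cited.

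**Reporting elsewhere.** Section 8.4.2 requires pregnancies and their outcomes to be reported during the study and for 6 weeks after the last osimertinib dose. Section 5.3.2 sets the same 6 weeks for female contraception, counted from stopping study treatment. Section 8.4.2.2 asks for follow-up of partner pregnancies "occurring from the date of the first dose until 6 months after the last dose", qualified as something to be done where feasible and with the partner's consent. Appendix A 3 provides a consent form for the case where a patient's "partner becomes pregnant during or within 6 months after the study, the partner is asked to sign".

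**Male precautions.** Section 5.3.2 requires condom use with a partner of childbearing potential "during the study and for 24 weeks after discontinuing study treatment", and adds: "Male patients should refrain from donating sperm from the start of dosing until 24 weeks after discontinuing study treatment". Inclusion criterion 19 instead asks men to accept "barrier contraception during the study and for 6 months following discontinuation of study drug", and continues: "Patients should refrain from donating sperm from the start of dosing until 6 months after discontinuing study treatment". Section 8.4.2.2 agrees with criterion 19: "Male patients should refrain from fathering a child or donating sperm during the study and 6 months following the last dose".

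**The concern.** Two sets of operative safety rules disagree.

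The more important one is the reporting window. The protocol requires contraception for a period after the last dose because of drug exposure, and in its main pregnancy section it collects pregnancies over that same period. For patients treated beyond the cut-off, the rule written specifically for them stops earlier. A site following Section 6.7 could leave an exposed pregnancy unreported while the contraception requirement is still running.

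The second is the length of the male precautions. A man can be enrolled on a 6-month undertaking and then be counselled from Section 5.3.2 to stop at 24 weeks. Following the longer period satisfies both rules, but the protocol does not say so, and sites may give different end dates.

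**Working it through.** The plan gives no calculated figure to reproduce. The check converts each stated window to days after the end of dosing and compares them.

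| Rule | Section | Stated | Days |
|---|---|---|---|
| Pregnancy reporting, treated after cut-off | 6.7 | 30 days | 30 |
| Pregnancy reporting, general | 8.4.2 | 6 weeks | 6 × 7 = 42 |
| Female contraception | 5.3.2 | 6 weeks | 42 |
| Male condom use and sperm donation | 5.3.2 | 24 weeks | 24 × 7 = 168 |
| Male contraception and sperm donation | 5.1, criterion 19 | 6 months | 181–184 |
| Fathering a child and sperm donation | 8.4.2.2 | 6 months | 181–184 |
| Partner-pregnancy follow-up | 8.4.2.2 | 6 months | 181–184 |

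Six calendar months last 181 to 184 days depending on the start date; the average is 6 × 365.25 / 12 = 182.6 days.

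**Reporting gap under Section 6.7**

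- Against the 6-week window: 42 − 30 = 12 days (days 31 to 42).
- Against the 6-month partner window, if Section 6.7 covers partners: 181 − 30 = 151 to 184 − 30 = 154 days.
- Against the shorter male precaution period in Section 5.3.2, on the same condition: 168 − 30 = 138 days. This sets a reporting window against a contraception window, so it shows only that reporting would stop while precautions continue.

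**Male precaution gap**

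- 181 − 168 = 13 to 184 − 168 = 16 days.
- Four sentences give 6 months after treatment (two in criterion 19, two in Section 8.4.2.2) and two give 24 weeks (both in Section 5.3.2). Appendix A 3 also uses 6 months, but counts from the study rather than the last dose, so it is only indirect support. Section 5.3.2 is the outlier.

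**Does another rule cover days 31 to 42?**

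- Section 4.1.1 keeps SAE reporting alive for patients treated past the cut-off and asks investigators to notify possibly related SAEs learned of later. Under Section 8.4.2.1 a pregnancy is not ordinarily an AE, so an ongoing one does not trigger this.
- Section 8.4.2 classes abnormal pregnancy outcomes as SAEs. That catches some harmful outcomes, but not a pregnancy still in progress.
- Section 8.4.2.1 requires outcomes to be followed after a patient leaves the study. That helps only once the pregnancy is known.
- Section 6.7 defines the last patient's last visit as the end of that patient's treatment. For that patient, the part of Section 8.4.2 that applies during the study gives no cover after dosing stops; only the post-dose window does.

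**A related anchor.** Section 8.4.2 counts its 6 weeks from the last osimertinib dose. Sections 6.7 and 7.1 allow savolitinib alone, and a patient on savolitinib plus placebo who never crossed over has no on-study osimertinib dose to count from. Section 5.3.2 counts female contraception from stopping study treatment, so the two 6-week periods need not coincide.

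**The case against.** The strongest reply is that Section 6.7 never says it overrides Section 8.4.2. The general rule carries no exception for patients treated after the cut-off, and Section 6.7 keeps the study open until the last patient has been treated, so the longer windows can be read as still applying. On that reading there is an ambiguity, not a shortened window. Abnormal outcomes remain reportable as SAEs, and the residual gap narrows mainly to a normal or unresolved pregnancy first detected in a 12-day interval. The partner figures depend on Section 6.7 covering partners, which it does not state, and partner follow-up is in any case on a where-feasible basis.

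On male precautions, the difference is about two weeks, 24 weeks may simply be a loose rendering of 6 months, and a man who keeps to criterion 19 automatically satisfies Section 5.3.2. The consent form may state a single period, but its pages are not available here.

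Much of this limits the size of the problem without removing it. Section 6.7 is the rule written for this period, it names pregnancies explicitly, and it cross-refers to nothing. The database is then closed, whereas Section 8.4.2.1 routes pregnancy reports through the eCRF, so sites will naturally work from Section 6.7. None of the safeguards makes a patient's ongoing pregnancy first found on days 31 to 42 reportable under that rule. The point about partners stands: those figures are conditional.

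**Conclusion.** The concern holds. The firm result is that, for patients treated after the final cut-off, the stated pregnancy-reporting period ends 12 days before the window in Section 8.4.2 and before the female contraception period ends. If Section 6.7 is also meant to cover partner pregnancies, the shortfall against Section 8.4.2.2 is 151 to 154 days. The male precaution conflict is real but minor, at 13 to 16 days.

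This rests on reading Section 6.7 as the operative rule after the cut-off and on 6 months meaning calendar months. Only patients still on treatment after that date are affected by the reporting point; the documents give no number for them. Nothing here affects eligibility thresholds, dosing, efficacy endpoints, sample size, power or alpha. It should be corrected because it is a conflict between safety rules that sites must act on.

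**What to change.** - **Section 6.7:** keep 30 days for SAEs and overdoses, and take pregnancies out of that sentence. Add: *Pregnancies will be reported per Sections 8.4.2 and 8.4.2.2 (patients: 6 weeks after the last dose; partners: 6 months after the last dose).*
- **Section 5.3.2:** replace 24 weeks with 6 months in both the condom sentence and the sperm-donation sentence for men.
- **Section 8.4.2:** count the 6 weeks from the last dose of study treatment instead of osimertinib, so that the window also works for patients on savolitinib alone and matches the female contraception period.

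The lengths are ones the protocol already uses. The cost is a wording change in three sections and a note to sites. Passive pregnancy reporting runs longer for patients treated after the cut-off: 12 more days for their own pregnancies and, where the partner agrees, up to 6 months for partner pregnancies. No visits or tests are added.
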